### *Rationale for treatment regimen estimand:*

The treatment regimen estimand estimates how participants with T2D are treated in clinical practice and takes into account both efficacy and safety.

### ***Registration for countries outside the United States***

The *primary* clinical question of interest is:

What is the treatment difference between LY3209590 and insulin glargine in change from baseline at Week 26 in HbA1c in study eligible participants who adhere to the randomized treatment without an intercurrent event during the study treatment period?

The ***efficacy estimand*** will be used for the primary objective and is described by the attributes in this table.

Efficacy Regimen Estimand Attribute	Description
Treatment condition	randomized treatment
Population	targeted study population. See Section 9.2 for details.
Endpoint	change from baseline to Week 26 in HbA1c.

Remaining intercurrent events	none. The 2 intercurrent events, treatment discontinuation for any reason and initiation of rescue therapy, are handled by the hypothetical strategy, for example, the potential outcome for those participants if the intercurrent events have not occurred will be estimated.
Population-level summary	difference in mean changes between treatment conditions.

*Rationale for efficacy estimand:* The treatment efficacy estimand supports the interpretation of the treatment effect as participants adhere to study treatment.

### **Secondary estimands (for multiplicity-adjusted objectives)**

The superiority test in change from baseline to Week 26 in HbA1c will also be based on the primary estimands described above.

The percentage of participants achieving HbA1c <7% at Week 26 without nocturnal hypoglycemia (<54 mg/dL [3.0 mmol/L], or severe) during treatment phase up to Week 26 will be based on a composite estimand. The details will be described in the SAP.

The participant-reported clinically significant nocturnal hypoglycemia (<54 mg/dL [3.0 mmol/L], or severe) is one of the safety measures for the study. The event rate will be based on all available data during the specific analysis period. Relative rate between randomized treatment groups will be used for treatment comparison.

## 4. Study Design

### 4.1. Overall Design

This is a Phase 3, parallel-design, open-label, randomized controlled trial that will evaluate the efficacy and safety of LY3209590 compared to insulin glargine in participants with T2D who are on once- or twice-daily basal insulin and at least 2 injections per day of prandial insulin prior to entering the study. Participants will continue prior stable therapy with 0 to 3 allowed noninsulin diabetes medications during the study.

The study consists of a 1-week screening period, a 2-week lead-in period, a 26-week treatment period, and a 5-week safety follow-up period.

#### **Screening and Lead-In**

##### ***Visit 1: Screening***

Interested participants will sign the appropriate informed consent document(s) prior to initiating any procedures.

The investigator will review medical history, symptoms, risk factors, and other inclusion and exclusion criteria prior to any diagnostic procedures. If the participant is eligible after this review, then the site will perform the diagnostic procedures to confirm eligibility.

##### ***Visit 2: Lead-In***

Participants will receive their e-diary, glucometer, and the CGM system.

Participants will receive training on

- diabetes self-monitoring and management
- study glucometer
- CGM
- electronic study diaries, and
- study requirements.

The CGM sensor will be inserted at Visit 2, and participants will be required to wear the sensor when indicated per the SoA.

Starting with Visit 2, participants must measure their FBG levels each day when possible or at a minimum 3 times per week. Starting with Visit 2, participants are strongly encouraged to measure 4-point SMBG profiles at least 3 times per week. Participants will use the study supplied glucometer and e-diary for data collection throughout the study.

Participants will continue their current insulin therapy until randomization. On the day of Visit 3, participants who typically take a morning dose of basal insulin should omit their morning dose of basal insulin as they will receive basal insulin at Visit 3.

#### **Treatment period**

##### ***Visit 3 (Week 0): Randomization***

This is the general flow for Visit 3:

- Study personnel confirm enrollment criteria

- Participants are randomly assigned to an intervention group
- Study personnel complete baseline procedures and sample collection
- Study personnel will provide dosing training
- Study personnel or the participant will administer the first study dose of LY3209590. Insulin glargine can be taken at the site or after the visit depending upon whether the study visit timing coincides with the participant's usual time to administer basal insulin. Administered insulin doses will be entered into the e-diary
- Study personnel train participants on administering insulin lispro at mealtimes
- Study personnel will download the CGM
- Participant will continue CGM wear per the SoA, and
- Study personnel complete all visit procedures.

All participants will be treated with insulin lispro as prandial insulin throughout the treatment period as described in Section 6.5.3. Participants assigned to insulin glargine will administer glargine daily after Visit 3.

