### **Overall design**

#### ***Blinding***

This is an open-label study. Investigators, participants, and study-site personnel will be unblinded to the assigned treatment. To eliminate potential biases, designated members of the Lilly study team will remain blinded throughout the study (see Section 6.3). Only a minimum number of Lilly personnel will see the randomization table and treatment assignments before the study is complete.

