#### **8.1.2. Patient-reported Outcomes**

The self-administered questionnaires will be translated into the native language of the region and administered at the site during the designated visits in the SoA.

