##### **Order of administering the questionnaires during the visit**

If the participant is not adversely affected by their fasting condition, the questionnaires should be completed before the participant has discussed their medical condition or progress in the study with the investigator or study personnel.

Preferred administration order of these questionnaires is

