TEAEs	The baseline period includes the screening/lead-in period up to the first dose of study treatment (AE Start Relative to Exposure Assessment in CRF is used to determine).	Safety analysis period starts after the first dose and ends at the last visit in the study including safety follow-up period.
Safety laboratory tests, vital signs and body weight	
The baseline will be the last non-missing assessment prior to or on the day of first dose of study treatment
 
Planned measurements at scheduled visits will be included.
	
All scheduled visits after the day of first dose up to Visit 802 for MMRM or ANCOVA
 
Planned measurements at scheduled visits will be included.

Analysis	Baseline Observations	Post-Baseline Observations
laboratory values elevated or low, vital signs and body weight categorical measures	
Starts from the screening visit and ends prior to or on the day of first dose of study treatment.
 
All available measurement at scheduled and unscheduled visits will be included. The baseline for weight will be the last non-missing value during the baseline period
	
Starts after the day of first dose of study treatment and ends at the last visit in the study including both treatment period and follow-up period.
 
All available measurement at scheduled and unscheduled visits in the specified analysis period will be included.

Anti-LY3209590 antibody	The baseline will be the last non-missing assessment prior to or on the day of first dose of study treatment	All scheduled and unscheduled measurement after the day of first dose of study treatment .
Patient-reported outcomes	The baseline will be the data collected at Visit 3	Last collection after Visit 3

Abbreviations: ANCOVA = analysis of covariance; CGM = continuous glucose monitoring; CRF = case report form; EAS1 = efficacy analysis set 1; EAS2 = efficacy analysis set 2; MMRM = mixed model repeated measurement; TEAE = treatment-emergent adverse event.

All analyses will be implemented using SAS Enterprise Guide Version 7.1 or above.

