##### 4.5.3.2. EQ-5D-5L

The EQ-5D-5L (EuroQol 2019) is a standardized 5-item self-administered instrument for use as a measure of health outcome. It provides a simple descriptive profile and a single index value for health status that can be used in the clinical and economic evaluation of health care as well as population health surveys. The EQ-5D-5L assesses 5 dimensions of health:

- mobility
- selfcare
- usual activities
- pain/discomfort
- anxiety/depression

The 5L version, scores each dimension at 5 levels:

- no problems
- slight problems
- moderate problems
- severe problems
- unable to perform/extreme problems

In addition to the health profile, a single health state index value can be derived based on a formula that attaches weights to each of the levels in each dimension. This index value ranges between less than 0 (where 0 is a health state equivalent to death; negative values are valued as worse than dead) to 1 (perfect health).

The second part of the questionnaire consists of EQ Visual Analog Scale (VAS) which records the respondent's self-rated health status. The participant rates his or her perceived health from 0 (the worst imaginable health) to 100 (the best imaginable health). In conjunction with the health state data, it provides a composite picture of the respondent's health status.

The frequency and proportion of each level for a given item will be summarized by study treatment for the scheduled visit. The last non-missing postbaseline observations up to Week 26 (Visit 23) on EQ-5D-5L index, EQ VAS score and their change from baseline will be analyzed by an ANCOVA model using the independent variables of treatment, strata (country, baseline HbA1c stratum ( $<8.0\%$ ,  $\geq 8.0\%$ ), and routine use of personal CGM or FGM at randomization), and baseline value of the dependent variable.

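### The Visit 3 flow lists baseline procedures after randomization in an open-label trial, so the only baseline EQ-5D-5L can be answered with the arm known

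*Protocol*

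**What the plan says.** Protocol 4.1 introduces its Visit 3 list with "This is the general flow for Visit 3". Once eligibility is confirmed, the next item is "Participants are randomly assigned to an intervention group", followed by "Study personnel complete baseline procedures and sample collection". Training and the first dose come later in the list.

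The Blinding paragraph of Protocol 4.2 says: "Investigators, participants, and study-site personnel will be unblinded to the assigned treatment".

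Protocol 8.1.2 has the questionnaires self-administered and "administered at the site during the designated visits in the SoA". It gives one timing rule within a visit. Provided that fasting is not troubling the participant, "the questionnaires should be completed before the participant has discussed their medical condition or progress in the study with the investigator or study personnel". The rule mentions neither randomization nor learning the assignment.

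The SoA schedules one baseline EQ-5D-5L, and its comment on that row concerns only electronic capture. For patient-reported outcomes, the baseline table in SAP 4.1 says: "The baseline will be the data collected at Visit 3". SAP 4.5.3.2 analyzes the index, the VAS and their changes by ANCOVA with treatment, the strata "and baseline value of the dependent variable". Protocol Section 3 lists change in EQ-5D-5L among the tertiary endpoints.

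**The concern.** A baseline covariate should be fixed before anything that differs between the arms can act on it. A site that works down the Visit 3 list in order would randomize first and collect the questionnaire afterwards, and nothing keeps the assignment from the participant in between. The EQ-5D-5L includes an anxiety/depression item and a self-rated health scale from 0 to 100. News of the allocation could plausibly move either one, and need not move them equally for a weekly and a daily insulin.

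No earlier EQ-5D-5L value is available to fall back on. At stake are the adjusted EQ-5D-5L comparison and the reading of EQ-5D-5L balance at baseline. The other questionnaires (DID-EQ and the two Basal Insulin Experience items) have no baseline collection in the SoA and are not involved.

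**Working it through.** The documents give no figure on this point to reproduce. The check has two parts: whether the text allows a post-allocation baseline, and what that would do to the estimate.

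**Order of events**

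1. Protocol 4.1 puts randomization second and baseline procedures third.
2. Protocol 4.2 and 6.3 make the trial open label for participants and sites, so the arm can be known from step 2 onward.
3. Protocol 8.1.2 ties the questionnaires to discussion of the participant's condition or progress. A participant may know the arm without having had that discussion, so a site can follow this rule and still collect the form after allocation.
4. Where the SoA comments on sample timing at Visit 3, the reference is dosing: antibody and biomarker samples before it, the PK sample at least 15 minutes after it. The SoA does name randomization as a limit for confirming eligibility. It sets no such limit for the EQ-5D-5L.
5. SAP 4.1 accepts any Visit 3 value as the baseline.

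**Effect on the estimate**

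Let B be the baseline score that would have been given without knowledge of the arm, T the arm indicator (1 = LY3209590), and Y = a + βB + τT + error the Week 26 score. If knowledge of the arm shifts the recorded baseline by d in one arm relative to the other, the recorded value is B* = B + dT. Substituting B = B* − dT:

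- Y = a + βB* + (τ − βd)T + error, so ANCOVA estimates τ − βd. The bias is −βd, for the score and for its change alike.
- The unadjusted difference in change estimates τ − d. The bias is −d.

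In index points, with assumed β = 0.6:

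- d = 0.01 gives a bias of −0.6 × 0.01 = −0.006.
- d = 0.03 gives a bias of −0.6 × 0.03 = −0.018.

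In SD units, a simulation (400,000 participants, true effect 0, baseline to Week 26 correlation ρ acting as the slope) gave these ANCOVA treatment differences:

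| ρ (assumed) | d = 0.1 SD | d = 0.2 SD | d = 0.3 SD |
|---|---|---|---|
| 0.3 | −0.030 | −0.058 | −0.094 |
| 0.5 | −0.051 | −0.098 | −0.154 |
| 0.7 | −0.071 | −0.138 | −0.214 |

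These match −ρd (for example, 0.5 × 0.2 = 0.10 and 0.7 × 0.3 = 0.21). The unadjusted difference in change was biased by about −d, from −0.10 to −0.31 SD. Baseline adjustment shrinks the bias without removing it. At d = 0 the formula gives no bias.

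The values of β, ρ and d are all assumptions; none is in the documents.

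**The case against.** The strongest reply is that Protocol 8.1.2 already deals with this. The Visit 3 list is only a general flow, does not name the EQ-5D-5L, and speaks of what study personnel complete, whereas the questionnaire is self-administered. Visit 3 also involves eligibility confirmation, adverse events, hypoglycemia history and an e-diary check. A site that puts the questionnaires ahead of any talk of condition or progress would normally finish the EQ-5D-5L before eligibility review, and so before allocation. This lowers the risk and stands to that extent. It does not close the gap: the rule is a recommendation, it depends on tolerating the fast at what is a fasting visit, and it says nothing about allocation.

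A second reply is that Protocol 4.1 does not say when the participant learns the arm. The first listed steps that must reveal it, dosing training and the first dose, come after baseline procedures. That is correct, so the point is about what can happen, not what must.

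Third, the Week 26 form is answered by people who have known their arm throughout, and reordering Visit 3 does nothing about that. This also stands. It is inherent in an open-label design, whereas the baseline exposure is avoidable.

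A reader might infer that the EQ-5D-5L comparison is biased and its baseline balance uninterpretable. The documents do not support that: they give no evidence of a shift, and the sizes above rest on assumed inputs. Nor do they support extending the worry to HbA1c, which is a central laboratory value that same-day knowledge of the arm should not materially alter.

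**Conclusion.** The concern holds as a minor, avoidable weakness. The stated order allows the only baseline EQ-5D-5L to be recorded after the arm is known, and no section requires otherwise. Any resulting bias in the ANCOVA estimate is about minus slope times d. That is 0.006 to 0.018 index points in size under the assumed slope of 0.6 and d of 0.01 to 0.03, or 0.03 to 0.21 SD under the assumed correlations of 0.3 to 0.7 and shifts of 0.1 to 0.3 SD.

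The direction is open. If allocation to weekly insulin raised baseline scores, the bias would run against LY3209590; if it lowered them, the bias would favor it. If sites collect the form before allocation, or if participants' answers do not respond to the news, there is no bias. The consequence is confined to a tertiary endpoint outside the multiplicity scheme in SAP 2.1. The primary and key secondary conclusions do not depend on it.

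**What to change.** State in Protocol 4.1, in Protocol 8.1.2 and in the SoA row for the EQ-5D-5L that the Visit 3 questionnaire is completed before the IWRS assignment is made or disclosed. Limit the sentence to this questionnaire. Simply exchanging the two items in the Visit 3 list would move all sample collection ahead of randomization and would conflict with the PK sample, which the SoA and Protocol 8.8 place after dosing. Sample timing should stay as it is.

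If enrollment is complete, compare eCOA completion times with IWRS randomization times where both are recorded. Report how many baseline forms followed allocation, and add to SAP 4.5.3.2 a sensitivity analysis that excludes them.

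The cost is one sentence in three places, with no added visit, procedure or participant. Protocol 10.1.1 requires IRB/IEC approval before amended study-design changes are implemented, so the text is best carried in an amendment made for other reasons. The SAP addition needs only a time comparison and one repeat of an existing model.

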#### ***Visit 4 (Week 1)***

Study personnel and participants complete all visit procedures described in the SoA.

Study personnel will provide dosing training and observe participants administering their second dose of LY3209590. Participants assigned to insulin glargine can continue routine daily administration.

#### ***Visit 5 through Visit 23 (Week 2 through Week 26)***

Study personnel and participants complete all visit procedures described in the SoA.

The participant's median FBG from the 3 most recent FBGs in the prior week will be used to titrate basal insulin dose adjustments throughout the study based on the study titration algorithm described in Section 6.5.1. Prandial insulin doses should be adjusted as needed.

Participants will collect blinded CGM for

- 4 weeks prior to Visit 7, and the site will download the CGM data at Visit 7
- 4 weeks prior to Visit 15, and the site will download the CGM data at Visit 15, and
- 4 weeks prior to Visit 23, and the site will download the CGM data at Visit 23.

The investigator or study staff will review participant e-diary compliance for

- SMBGs
- hypoglycemia events including related signs and symptoms, and
- dosing information, including date and time of doses.

#### ***Last study treatment visit: either Visit 23 (Week 26) or ED visit***

Participants should complete all visit procedures in a fasting state.

Participants will return unused study intervention to the investigative site.

Assessments for the transition to non-study diabetic treatment after the participant's last dose.

- The investigator will determine a participant's transition from study basal insulin to another basal insulin. Investigators will also start the participant on a non-study prandial insulin (see Section 6.6.1).
- Participants will continue their concomitant antihyperglycemic medications at the discretion of the investigator.

#### ***Safety follow-up visits 801 and 802***

Study personnel and participants complete all visit procedures described in the SoA.

Participants will collect blinded CGM for 4 weeks following Visit 23, and the site will download the CGM data at Visit 802.

The investigator will follow-up on the participant's transition from study treatment to another non-study diabetic treatment.

Participants will return study devices at the final study visit.

## **4.2. Scientific Rationale for Study Design**

### **Primary endpoint**

The primary efficacy measurement is HbA1c, a widely used measure of glycemic control that reflects a cumulative history of glucose levels in the preceding 2 to 3 months.

### **Overall design**

#### ***Blinding***

This is an open-label study. Investigators, participants, and study-site personnel will be unblinded to the assigned treatment. To eliminate potential biases, designated members of the Lilly study team will remain blinded throughout the study (see Section 6.3). Only a minimum number of Lilly personnel will see the randomization table and treatment assignments before the study is complete.

#### ***Study duration***

The treatment duration is a reasonable timeframe to observe the effects of LY3209590 compared to insulin glargine. The primary endpoint at Visit 23 (Week 26) is based on participants reaching a stable insulin dose in order to achieve glycemic stability approximately 12 weeks in advance of the 26-week primary endpoint. HbA1c is the primary endpoint and reflects glycemic control from the prior 8 to 12 weeks.

The follow-up visits after the last dose are designed to capture any additional safety signals and to monitor the transition from study basal insulin to non-study basal insulin.

#### ***Comparator***

Insulin glargine was chosen as the comparator because it is a widely used basal insulin.

### Collection of race and ethnicity data

In this study, collection of demographic information includes ethnicity (where permissible) and race. The scientific rationale is based on the need to assess variable response in safety or efficacy based on race or ethnicity. This question can be answered only if all the relevant data are collected.

### 4.3. Justification for Dose

The dosing guidance for starting doses and dose titrations of LY3209590 and insulin glargine are derived based on findings from Phase 2 studies and model-based simulations. These data informed the development of a titration algorithm to safely and efficiently initiate and guide LY3209590 and insulin glargine dose adjustments to achieve the same glycemic goals of FBG between 80 and 120 mg/dL (4.4 and 6.6 mmol/L) while minimizing hypoglycemia risk.

See Section [6.5](#) for dose modification and titration details.

#### LY3209590

##### *Initial loading dose*

The initial loading dose aims to optimize and accelerate glycemic control by allowing participants to reach a steady-state concentration faster. The use of a single one-time-only loading dose enables participants to achieve concentrations close to steady state within a few days rather than a period of weeks. This approach minimizes the risk for hyperglycemia during transition to LY3209590 while reaching steady state. In all cases, starting doses will be based upon existing total daily basal insulin doses.

This approach is supported by the Phase 2 Study BDCM and PK model-based simulations.

Details on deriving the loading dose are described in Section [6.5](#).

